- Any additional data that seems relevant for this study.

Section 9.4 Data sources

Reporting of vaccine-exposed pregnancies to the Registry is voluntary. Registration can be initiated from a HCP or from a consumer, in which case permission is requested to obtain confirmation and follow-up from their HCP. *Follow-up from the*

HCP of the infant post birth 6 and 12 months will be performed when the contact details are available and with consumer's permission. A toll-free telephone number for reporting AEs and vaccine-exposed pregnancies to the Registry is listed in the product information leaflet and on the GSK Registry website. Retrospective post-marketing reports and relevant scientific publications are potential sources of supplementary information.

Section 9.6.1 Data collection

Initial and follow-up data will be collected using questionnaires. Initial data will be collected before the outcome is known. Follow-up of cases will be performed at the following timepoints:

- ***For consumer reports:***
 - ***At initial notification of pregnancy exposure: 2 attempts at 4-6 week intervals will be made to obtain more information about the pregnancy (e.g. estimated time of delivery (EDD) and/or last menstrual period (LMP) and to obtain permission to contact the patient's HCP***
 - ***Within 2 months after EDD, 1 additional attempt is made if permission to contact the patient's HCP has not already been granted to obtain more information about the pregnancy and obtain the permission to contact the patient's HCP.***
 - ***Within 2 months after EDD (and if the patient has not previously provided the contact information for the infant's HCP): 2 attempts at 4-6 week intervals will be made for the prospective cases reporting a live birth to obtain the contact information of the HCP supervising the health of the infant.***
- ***For the HCP reports:***
 - ***At initial notification of pregnancy exposure or once permission has been granted for reports initially received from a consumer, two attempts at 4-6 week intervals will be made to obtain more information via pregnancy follow-up form.***
 - ***Within 2-3 months of the EDD, to ascertain outcome. At least three ~~Two~~ follow-up attempts to obtain outcome information will be made before any case is considered lost to follow-up.***
- ***An additional follow-up attempt will be done for all the live births approximately 6 months and 12 months after the EDD to ascertain the presence of birth defects not diagnosed at the time of the initial follow-up. This follow-up will be done for the prospective reports if the consumer has granted the permission and when the contact details of the HCP attending the infant are available.***

Section 9.6.2 Processing of reports

~~Initial~~ Reports are entered into the GSK safety database by **GSK Call Center Case Management Group (CMG)** using existing mechanisms and practices. Medical Dictionary for Regulatory Activities (MedDRA) is used in the database to code AEs.

Follow-up is conducted by the **CMG**. The HCP is contacted if she/he requests or if initial information is insufficient or needs clarification. ~~The HCP is encouraged to keep a copy of the initial completed form in the patient's chart. The follow-up of cases is performed as described in section 9.6.1.~~

Section 9.6.2.1 Solicitation of outcome

~~As explained in section 9.6.1, within three~~ **two** months after the EDD and if the HCP has not already provided the **pregnancy** outcome, she/he is sent an outcome form (questionnaire), ~~along with a copy of the initial completed pregnancy form.~~ The mode of communication is ~~the one through which the initial information was received (telephone, fax, or postal mail)~~ **generally via standard letter.**

~~Two~~ **At least 3**, attempts are made to secure the outcome information from the HCP **via standard letter**. ~~The second and third attempts utilize all modes of contact available (mail, fax, telephone). If outcome is not received from the HCP and contact information is available for the patient, she is then contacted by mail or fax.~~

~~In the event of an abnormal outcome~~ **For the live births** and with the mother's permission, attempts are made to solicit information from the pediatrician and/or other specialists who have provided healthcare/consultation to the child **until 12 months of age.**

Section 9.6.2.2 Classification of outcome

This Registry uses the term 'birth defects' for outcomes sometimes referred to as 'congenital anomalies'. For purposes of analysis, pregnancy outcomes are dichotomized according to the presence or absence of birth defects. ~~The latter group is~~ **Pregnancy outcomes are** further categorized as: 1) live births, 2) spontaneous abortions (i.e., pregnancy losses), 3) **Elective**/induced abortions 4) **and Fetal deaths/Stillbirths.**

This Registry adopts a definition of a child with a birth defect as any live or stillborn neonate with a structural or chromosomal abnormality diagnosed before 6 years of age. The Registry employs a conservative approach of including all morphologic anomalies, including minor ones, as birth defects.

To provide consistency in the definitions of major defects in this Registry, CDC MACDP criteria are used for the classification of defects [CDC, 2008; Correa-Villasenor, 2003]. Some of the conditions excluded from the MACDP criteria for major structural defects may actually have major clinical, functional, or genetic significance. Therefore, minor malformations not appearing in the CDC inclusion list may be classified as birth defects in this Registry. In addition, CDC guidelines disqualify as defects those findings that are present in infants delivered at less than 36 weeks of gestation and are attributable

to prematurity itself, such as a patent ductus arteriosus or inguinal hernias. Infants with infectious conditions (e.g., neonatal sepsis) or isolated biochemical abnormalities (e.g., hyperbilirubinemia) are classified as being without birth defects unless there is a possibility that the condition reflects an unrecognized congenital abnormality. All other congenital abnormalities are included in the 'birth defects' category, regardless of whether the neonate is delivered alive, including structural defects in neonates delivered prior to 20 weeks of gestation or weighing less than 500 g.

Section 9.7 Data analysis

Pregnancy outcomes include spontaneous abortion (pregnancy loss before ~~22~~ 20 weeks gestation), fetal deaths/stillbirths (loss at or after ~~22~~ 20 weeks gestation), elective/~~therapeutic~~ **induced** abortions and live births. Gestational weeks are counted from the date of the LMP. The second trimester is considered to begin at week 14 and the third trimester begins at week 28. The presence or absence of birth defects or other abnormalities is evaluated within each of the preceding outcome categories.

Pregnancy outcomes are stratified by the trimester of exposure, with an additional stratum for preconception exposure with no subsequent administration of vaccine during pregnancy. Reports of multiple exposures during a pregnancy (i.e., multiple administrations of *Boostrix*) are classified by the earliest trimester of exposure. When exposure occurs before and after conception, the exposure is classified by the dose administered after conception. The calculations of risk for birth defects are made by dividing the number of infants with birth defects by the total number of infants with and without birth defects. ~~An exact 95% confidence interval is calculated using standard statistical software.~~ **Given the descriptive nature of this study, confidence intervals will not be calculated.** The outcomes of the study will be assessed against known rates from an external reference group for the likelihood of a safety signal warranting further investigation.

Section 12 Plans for disseminating and communicating study results

Study information from this protocol will be posted on publicly available clinical trial registers following finalization of the protocol and, whenever possible, before initiation of the study.

GSK plans to continue the Registry for 5 years. Summary reports will be written annually and will be submitted with the Periodic Benefit-Risk Evaluation Report **and the DSUR** for *Boostrix*. A final report will be written and submitted ~~after 5 years~~ **within one year of completion of the five-year period as described in Section 6**. After submission of the final report, GSK will continue the Registry pending CBER review of the report and determination whether the Registry can be discontinued.

Summary results of observational studies that are designed to inform the safety or effectiveness, including cost-effectiveness, of GSK vaccines/products as used in ordinary clinical practice are publicly registered within **& 12** months of completion of the analysis. GSK also aims to publish the results of these studies in the ~~searchable~~ **indexed**, peer reviewed scientific literature; manuscripts are submitted within 18 months of the completion of the analysis.

Section 13 References

EMA 2006.

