1. PASS INFORMATION

Title	Boostrix Pregnancy Registry: a prospective, exploratory, cohort study to detect and describe any abnormal pregnancy outcomes in women intentionally or unintentionally vaccinated with Boostrix during pregnancy or within 28 days preceding conception.
Protocol version identifier	201327 (EPI-PERTUSSIS-028 VS US PR)
Date of last version of the protocol	Amendment 1 Final: 05 October 2017
EU PAS Register No	Not applicable
Active substance	J07AJ52, bacterial vaccine, pertussis vaccines
Medicinal product	Boostrix, Tetanus Toxoid, Reduced Diphtheria Toxoid and Acellular Pertussis Vaccine, Adsorbed
Product reference	Not applicable
Procedure number	Not applicable
Marketing Authorization Holder	GlaxoSmithKline (GSK) Biologicals [name]
Joint PASS	No
Research question and objectives	
Co-primary objectives
 
 To describe the characteristics of registered pregnancies (women vaccinated with Boostrix during pregnancy or within 28 days preceding conception) with any abnormal pregnancy outcomes.

CONFIDENTIAL

201327 (EPI-PERTUSSIS-028 VS US PR)

Protocol Amendment 1 Final

	
To assess the proportion of registered pregnancies (women vaccinated with Boostrix during pregnancy or within 28 days preceding conception) with any abnormal pregnancy outcomes.
Country of study	United States

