6. MILESTONES (AMENDED ON 05 OCTOBER 2017)

Milestone (Including Data Lock Point (DLP) of each report)	Planned Submission date
Start of data collection	Q1 2014 ^a
End of data collection	2 August 2019 ^b
Annual report 1 (DLP: 2 August 2015)	Q2 2016
Annual report 2 (DLP: 2 August 2016)	Q2 2017
Annual report 3 (DLP: 2 August 2017)	Q2 2018
Annual report 4 (DLP: 2 August 2018)	Q2 2019
Annual report 5/Final report (DLP: 2 August 2019)	Q2 2020 ^c
Registration in the EU PAS register	Q1 2014

^a The Registry was originally initiated on 03 May 2005, as part of a program of enhanced pharmacovigilance. Following new European Union Pharmacovigilance legislation, pregnancy registries are to be considered as post-authorization safety studies (PASS). The ongoing Registry will therefore be converted into a PASS. GSK plans to continue the Registry for a minimum of 5 years, starting Q1 2014. **Summary reports will be written annually and will be submitted with the Periodic Benefit-Risk Evaluation Report (PBRER) and the Development Safety Update Report (DSUR) for Boostrix.**

^b After submission of the final report, GSK will continue the Registry pending Center for Biologics Evaluation and Research (CBER) review of the report and determination whether the Registry can be discontinued.

^c **Since the annual reports also contain cumulative data, the last annual report (with DLP: 2 August 2019) will serve the purpose of the Final report.**

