9.2.4. Study period (Amended on 05 October 2017)

The Registry was originally initiated on 03 May 2005, as part of a program of enhanced pharmacovigilance, and converted into a PASS *in Q1 2014*. GSK plans to continue the Registry for a minimum of 5 years, starting Q1 2014. After submission of the final report, GSK will continue the Registry pending CBER review of the report and determination whether the Registry can be discontinued.

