9.6. Data management

9.6.1. Data collection (Amended on 05 October 2017)

Initial and follow-up data will be collected using questionnaires. Initial data will be collected before the outcome is known. Follow-up of cases will be performed at the following timepoints:

- ***For consumer reports:***
 - ***At initial notification of pregnancy exposure: 2 attempts at 4-6 week intervals will be made to obtain more information about the pregnancy (e.g. estimated time of delivery (EDD) and/or last menstrual period (LMP) and to obtain permission to contact the patient's HCP***
 - ***Within 2 months after EDD, 1 additional attempt is made if permission to contact the patient's HCP has not already been granted to obtain more information about the pregnancy and obtain the permission to contact the patient's HCP.***
 - ***Within 2 months after EDD (and if the patient has not previously provided the contact information for the infant's HCP): 2 attempts at 4-6 week intervals will be made for the prospective cases reporting a live birth to obtain the contact information of the HCP supervising the health of the infant.***

- ***For the HCP reports:***
 - ***At initial notification of pregnancy exposure or once permission has been granted for reports initially received from a consumer, two attempts at 4-6 week intervals will be made to obtain more information via pregnancy follow-up form.***
 - Within 2 months of the EDD, to ascertain outcome. ***Two follow-up*** attempts to obtain outcome information will be made before any case is considered lost to follow-up.
- An additional follow-up ***attempt*** will be done for ***the*** live births approximately 6 months and 12 months after the EDD to ascertain the presence of birth defects not diagnosed at the time of the initial ***pregnancy outcome***. ***This follow-up will be done for the prospective reports if the consumer has granted the permission and when the contact details of the HCP attending the infant are available.***

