According to the initial version of the protocol, additional follow-up questionnaires should be sent for all live births approximately 6 months and 12 months after EDD to ascertain the presence of birth defects not diagnosed at the time of the initial follow up. However neither of these follow-up questionnaires were implemented as of this protocol amendment.

GSK Biologicals acknowledges the importance of this information and intends to implement both 6- and 12-month follow-up attempts prospectively. The data collection form for 6- and 12-month follow-ups will be developed in parallel to this protocol amendment. For the subjects already enrolled, there will be no attempt to collect the 6 and 12-month data as the likelihood of having appropriate contact details and/or receiving reliable data is low and such practice is likely to introduce recall bias, hence compromising the validity of the results.

Hence, the above proposed changes will only be applicable for patients to be enrolled after the approval of this protocol amendment (and the related documents/forms) when the pregnancy outcome is a live birth, the contact details of the HCP attending the infant are available and with the consumer's permission.

Originally, a signed consent form from pregnant subjects was only requested when these registered themselves into the registry, and to allow GSK to contact their HCPs. GSK will now also encourage HCPs who register their patients to provide these with the consent form. This consent will also allow to contact the HCP supervising the health of the infant up until 12 months after delivery (the updated consent form will now request contact information from HCP supervising the health of infant). This new consent form will be implemented for all prospective reports after the protocol amendment approval.

Gestational age cut-off for spontaneous abortions and stillbirths:

The 20 weeks' cut-off in gestational age has been replaced by 22 weeks based on WHO-ICD 10 noted in the EMA Guideline on pregnancy exposure [EMA, 2006], as per the standard definition used by GSK Biologicals. It is recognized that national regulations might be different.

Exclusion Criteria section:

The following sentence have been deleted from the exclusion criteria section
“Pregnancies in which prenatal testing indicates a normal pregnancy would also be excluded because inclusion of such pregnancies could potentially bias results toward a lower overall estimate of risk for defects”

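### Amendment 1 drops women still pregnant at its approval from the 6- and 12-month infant checks for reasons that do not apply to them, and Section 9 does not carry the restriction

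*Combined protocol and SAP*

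**What the plan says.** Annex 4, under its heading on additional follow-up at 6 and 12 months after EDD, records that "neither of these follow-up questionnaires were implemented as of this protocol amendment". For the future it says "For the subjects already enrolled, there will be no attempt to collect the 6 and 12-month data", and that the changes "will only be applicable for patients to be enrolled after the approval of this protocol amendment" and its forms, given a live birth, contact details for the infant's healthcare professional (HCP) and the consumer's permission. The reasons offered are that contact details or reliable data are unlikely to be available and that late collection invites recall bias. Ongoing pregnancies are not excepted. Annex 4 is the amendment record, but this paragraph sets the rule from approval onward and is not superseded text.

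The same heading explains that signed consent used to be sought only from women who registered themselves, to allow contact with their own HCPs. An updated form, for prospective reports after approval, will also cover the HCP supervising the infant.

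In the body, Section 9.6.1 provides a further attempt for "live births approximately 6 months and 12 months after the EDD to ascertain the presence of birth defects" not found earlier. It is limited to prospective reports with permission and infant-HCP details. Section 9.1.1 limits the checks by infant-HCP contact, and Section 9.6.2.1 seeks information from the child's doctors up to 12 months of age with the mother's permission. None of the three mentions the date of enrolment.

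Section 1 dates the amendment "Amendment 1 Final: 05 October 2017". Section 6 sets the final data lock at 2 August 2019.

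**The concern.** Recall bias and stale contact details are fair reasons not to chase checks whose dates have passed. They do not describe a woman who has not delivered. Her infant's forms would go out at the planned times, to a clinician, and the outcome letter of Section 9.6.2.1 has yet to be sent. For consumer reports, Section 9.6.1 also still has its post-EDD requests for permission and for the infant HCP's details ahead of it. The rule is keyed to the date of enrolment, whereas the reasons depend on whether the check date has passed.

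The infant checks exist to find defects missed at the pregnancy-outcome contact. Section 9.6.2.2 counts defects diagnosed up to 6 years of age, and Section 9.7 sets the registry's proportion against external rates, about 3% of live births by CDC criteria. Missed late diagnoses can only lower that proportion, which is the reassuring direction. There is also a practical gap: staff working from Section 9.6.1 would send forms that Annex 4 rules out.

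**Working it through.** The plan gives no figure for the share of infants to be checked, so there is none to reproduce. What follows is calendar arithmetic.

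**Inputs from the documents**
- Amendment date 5 October 2017 (Section 1). The approval date is not given and is taken as the same day; a later date is tried below.
- Final lock 2 August 2019 (Section 6): 666 days, or 21.9 months, after the amendment.
- Checks at 6 and 12 months after EDD (Section 9.6.1). A 12-month date by the lock needs EDD by 2 August 2018 (301 days, 9.9 months after the amendment). A 6-month date by the lock needs EDD by 2 February 2019 (485 days, 15.9 months).
- Accrual (Section 9.2.1.2): 391 prospective reports from 3 May 2005 to 2 August 2013, so 391/8.25 = 47.4 a year (3.95 a month). The expected ceiling is 100 a year (8.33 a month).

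**Assumptions**
- Accrual is constant.
- The lead L from enrolment to EDD is 1 to 7 months.
- Each check counts as done on its due date.
- All counts are registered pregnancies, before losses, permission and non-live outcomes.

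**Formulas.** A woman with EDD at time t after approval was enrolled at t − L, so she is excluded if t < L.
- Infants due after approval, 12-month check: L / 9.9. For the 6-month check: L / 15.9.
- All infants whose 12-month date lies between approval and lock: (12 + L) / 21.9. For the 6-month check: (6 + L) / 21.9.

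| Share excluded | L = 1 month | L = 7 months |
|---|---|---|
| Due after approval, 12-month | 1/9.9 = 10% | 7/9.9 = 71% |
| Due after approval, 6-month | 1/15.9 = 6% | 7/15.9 = 44% |
| All 12-month dates still ahead | 13.0/21.9 = 59% | 19.0/21.9 = 87% |
| All 6-month dates still ahead | 7.0/21.9 = 32% | 13.0/21.9 = 59% |

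**Counts**
- Undelivered at approval and excluded: L × monthly accrual, from 1 × 3.95 = 4 to 7 × 8.33 = 58.
- Eligible under the present rule for a 12-month check by the lock: (9.9 − L) × monthly accrual, from 2.9 × 3.95 = 11 to 8.9 × 8.33 = 74.

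**Who makes up the larger share.** Of the 13 to 19 excluded enrolment-months in the third row, 12 belong to infants already past EDD at approval, which is 12/19 = 63% to 12/13 = 92%. Women still pregnant supply the rest.

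**Sensitivity**
- Among infants due after approval, the excluded 12-month share passes one half only if L exceeds 301/2 = 150.5 days. That means registration before (280 − 150.5)/7 = 18.5 weeks.
- If approval came on 1 January 2018, 19.0 months remain to the lock. The first row becomes 1/7.0 = 14% to 7/7.0 = 100%, and the third 13/19 = 68% to 19/19 = 100%.
- With accrual growing 50% a year and registration at 36 weeks, the third row's lower end falls from 59% to 50%.

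**Effect of the fix.** Adding only women undelivered at approval takes the first row to 0% and the third to 12/21.9 = 55%.

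**The case against.** **Consent.** Permission to approach the infant's HCP is new with this amendment, so an enrolment-date cut lines up with the consent change. That stands as a reason why women already enrolled need a fresh request. It does not bar asking women who have not delivered, since the outcome contact is still to come.

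**Contact details.** A reader might infer that the sponsor already holds what it needs, because Section 9.2.5 requires an identified HCP. That is not supported. It need not be the infant's HCP, and the subject may be identifiable only through the HCP. For infants already born, the sponsor's doubt about contact details is plausible.

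**Size.** A reader might take 59% to 87% as the loss among women still pregnant. It is not: most of that share is infants already past EDD. Among infants due after the amendment, whether most are lost turns on gestational age at registration, which the documents do not give. For the 6-month check the range straddles one half.

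**Conflict.** A reader might infer a flat contradiction between body and annex. The body is silent on enrolment date and the annex adds one. This is a gap to reconcile, and if the body governs, the exclusion does not operate.

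**Importance.** The registry is descriptive, with no minimum sample size (Section 9.5) and no confidence intervals (Section 9.7). At the 3% background rate, 4 to 58 pregnancies imply 0.1 to 1.7 defects in all, only some diagnosed late. The analysis is cumulative: "The Registry was originally initiated on 03 May 2005", and Section 9.7 keeps the pregnancies reported before 2014. Under constant accrual, 4,839 days of EDDs run from that date to 2 August 2018. Following every infant whose 12-month date was still ahead would still leave 1 − 666/4,839 = 86% without an on-time 12-month check. This stands, and it limits the severity.

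**Conclusion.** The point holds as a should-fix. Annex 4 excludes women undelivered at approval on grounds that do not apply to them, and Sections 9.1.1, 9.6.1 and 9.6.2.1 do not carry the restriction. The loss best supported is 10% to 71% of the 12-month checks due by the lock among infants born after the amendment, about 4 to 58 pregnancies. The wider figures, 59% to 87% at 12 months and 32% to 59% at 6 months, are correct only for a group that also includes infants already born, where the sponsor's reasons carry some weight.

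All of these rest on constant accrual, approval on 5 October 2017 and the assumed lead. Later approval raises the shares; rising accrual or later registration lowers them. The documents do not support a stronger reading in which the rule invalidates the registry's results or in which changing it would close the gap in infant follow-up.

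**What to change.** In Section 9.6.1 and Annex 4, state one rule keyed to delivery and check date:

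- The 6- and 12-month forms apply to all prospective live births of women undelivered at approval of Amendment 1, whatever the enrolment date.
- For these women, request the updated consent and the infant HCP's details with the pregnancy-outcome contact, whether the report came from a consumer or an HCP.
- Extend the forms to infants already born whose check date is still ahead only where permission and infant-HCP details can be obtained.
- Keep the bar for check dates already passed.
- Flag responses by enrolment period in the reports.

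Align Sections 9.1.1 and 9.6.2.1 with this rule.

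The cost is wording, new permission requests, up to two attempts to obtain contact details, and up to two forms per infant. For women undelivered at approval that is at most 2 × 4 = 8 to 2 × 58 = 116 forms. Extending to infants already born brings in a further 12 × 3.95 = 47 to 12 × 8.33 = 100 pregnancies. Yield there is likely to be lower, and some of those infants would have a 12-month check without a 6-month one.
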